4.1. Inclusion Criteria

- 1) Age \geq 18 years.
- 2) The time from onset to randomization was within 12 hours.
- 3) Anterior circulation ischemic stroke was determined according to clinical symptoms and imaging examination.
- 4) Occlusion of the intracranial internal carotid artery, the M1- or M2-segment of the middle cerebral artery confirmed by CT angiography (CTA), MR angiography (MRA), or digital subtraction angiography (DSA).
- 5) Baseline National Institutes of Health Stroke Scale (NIHSS) ≥ 6.
- 6) Baseline Alberta Stroke Program Early CT Score (ASPECTS)<6.
- 7) Planned treatment with endovascular therapy (EVT).
- 8) Informed consent obtained from patients or their legal representative.

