4.4. Privacy Protection

completely stored in the hospital where they receive treatment, and laboratory test reports and other examination results will be recorded in the patients' medical records. Only the investigators, ethics committees, and food and drug administration departments of this study will be allowed to access patients' medical records. Any public reports on the results of this study will not disclose the personal identities of patients. We will make every effort to protect the privacy of patients' personal medical information within the limits allowed by law.

According to medical research ethics, apart from personal privacy information, trial data will be available for public inquiry and sharing. Inquiry and sharing will be limited to web-based electronic databases to ensure that no personal privacy information is leaked.

5. Sample Size Calculation

Based on the research results from published literature and combined with clinicians' experience, the 90-day mortality rates for the intravenous methylprednisolone sodium succinate + endovascular treatment group (experimental group) and the placebo + endovascular treatment group (control group) are estimated to be 29% and 38%, respectively. Assuming a 1:1 ratio for the sample sizes of the two groups, a two-sided α of 0.05, and a power of 80%, the estimated sample size is 856 patients. Considering an expected dropout rate of 5%, the maximum estimated sample size, calculated using PASS 15.0, is 902 patients, with 451 patients in each of the intravenous methylprednisolone sodium succinate + endovascular treatment group (experimental group) and the placebo + endovascular treatment group (control group).

6. Randomization

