10.2. Secondary Endpoints

10.2.1. Secondary Efficacy Endpoints

- 1) mRS score improvement at 90 ±7 days;
- 2) Proportion of patients with mRS score 0 to 4 at 90 ± 7 days;
- 3) Proportion of patients with mRS score 0 to 3 at 90 \pm 7 days;
- 4) Proportion of patients with mRS score 0 to 2 at 90 ± 7 days;
- 5) Proportion of patients with mRS score 0 to 1 at 90 \pm 7 days;
- 6) mRS score improvement at 1 year;
- 7) Proportion of patients with mRS score 0 to 2 at 1 year;
- 8) Proportion of patients with mRS score 0 to 1 at 1 year;
- 9) mRS score improvement at 5 years;
- 10) Proportion of patients with mRS score 0 to 2 at 5 years;
- 11) Proportion of patients with mRS score 0 to 1 at 5 years;
- 12) NIHSS score at 5-7 days or at early discharge;
- 13) Health-related quality of life [European Quality of Life Five-Dimension visual-analogue scale (EQ-5D VAS)] at 90 ± 7 days;
- 14) Proportion of patients with malignant cerebral edema within 48 hours after EVT
- 15) Proportion of patients with secondary decompressive craniectomy
- 16) EQ-5D VAS at 1 year
- 17) EQ-5D VAS at 5 years

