12.2.4. Missing Data

12.3. Statistical Analysis Methods

Statistical tests will be performed using a two-sided significance level of 0.05 for indicators evaluated with superiority. Differences with a P-value ≤ 0.05 will be considered statistically significant.

Statistical analysis will be conducted on baseline indicators (such as medical history) and demographic characteristics. Intent-to-treat analysis will be used for statistical analysis of trial efficacy, with the per-protocol dataset (i.e., data from patients who meet all trial protocol criteria) as a reference.

Quantitative data will be described using means, medians, standard deviations, maximum and minimum values, and 25th and 75th percentiles. Comparisons between two groups will be made using the independent t-test or Mann-Whitney U test. Categorical or ordinal data will be described using frequencies and proportions. Comparisons between two groups for categorical data will be made using the chi-square test or Fisher's exact test, and for ordinal data, the Mann-Whitney *U* test will be used.

Previous studies have suggested that the following factors may affect the 90-day mRS score, and this study plans to conduct subgroup analysis based on these variables.

- 1) Age;
- 2) Gender:
- 3) Time of onset;
- 4) NIHSS score:
- 5) ASPECTS score;
- 6) TOAST classification [22];
- 7) Vascular occlusion site;
- 8) Collateral circulation score:
- 9) Anesthesia method:
- 10) Intravenous thrombolysis.

13. Quality Control and Assurance

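### NIHSS at 5-7 days (secondary efficacy endpoint 12) has only unadjusted tests in section 12.3, so the baseline NIHSS held for every eligible patient goes unused and precision is lost

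*Combined protocol and SAP*

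**What the plan says.** Section 10.2.1, item 12, defines the endpoint as "NIHSS score at 5-7 days or at early discharge". It is a follow-up score, not a change from baseline. A note to Table 1 adds that the discharge value is used when the stay is shorter than 5 days.

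The tests are in section 12.3. For quantitative data: "Comparisons between two groups will be made using the independent t-test or Mann-Whitney U test". For other data: "Comparisons between two groups for categorical data will be made using the chi-square test or Fisher's exact test, and for ordinal data", where the sentence goes on to name the Mann-Whitney U test. The synopsis gives the same set of tests. Neither place mentions analysis of covariance, regression, covariate adjustment or change from baseline.

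Baseline NIHSS is available. Inclusion criterion 5 in section 4.1 is "Baseline National Institutes of Health Stroke Scale (NIHSS) ≥ 6", and Table 1 schedules the score at screening. Its only stated analytic use is as one of ten subgroup variables, introduced in section 12.3 by "the following factors may affect the 90-day mRS score, and this study plans to conduct subgroup analysis based on these variables".

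Section 12.1.1 says that a statistical analysis plan will be finalised before database lock and will set out the methods for the different indicators. That plan is not among the documents.

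**The concern.** Endpoint 12 is measured on a scale that is also recorded before treatment. Patients enter with NIHSS of 6 or more and no upper limit, so initial severity can vary widely. An unadjusted comparison leaves all of that variation in the error term. Randomisation is stratified by centre only (synopsis), so baseline severity is balanced by chance and not by design.

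Putting baseline NIHSS in the model removes the part of the outcome variance that it predicts. Leaving it out gives a wider confidence interval and a lower chance of detecting a real early neurological effect. The primary mortality result is not affected.

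**Working it through.** **The plan's own figure.** The only sample size is for 90-day mortality: 38% against 29%, 1:1 allocation, two-sided 0.05, "and a power of 80%, the estimated sample size is 856 patients" (section 5). With unpooled variance, n per arm = (0.38×0.62 + 0.29×0.71) × (1.960 + 0.842)² / 0.09² = 0.4415 × 7.849 / 0.0081 = 427.8. That rounds up to 428 per arm, or 856 in total. Then 428/0.95 = 450.5, so 451 per arm and 902 in total. The figure reproduces. It says nothing about NIHSS.

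**Inputs for endpoint 12**
- From the documents: two-sided 0.05, 1:1 allocation, 428 evaluable per arm.
- Assumed: correlation ρ between baseline and 5-7 day NIHSS, shown from 0.3 to 0.7.
- Assumed: power of the unadjusted test, 80% as reference, with other values shown.

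**All scores observed.** Adjusting for baseline multiplies the residual variance by 1 − ρ². For an effect that the unadjusted test detects with 80% power, adjusted power = Φ[(1.960 + 0.842)/√(1 − ρ²) − 1.960].

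| ρ | Variance removed | Adjusted power | Gain (points) |
|---|---|---|---|
| 0.3 | 9% | 83.6% | 3.6 |
| 0.4 | 16% | 86.4% | 6.4 |
| 0.5 | 25% | 89.9% | 9.9 |
| 0.6 | 36% | 93.8% | 13.8 |
| 0.7 | 49% | 97.5% | 17.5 |

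**Dependence on the reference power, at ρ = 0.5.** The gain is 8.1 points if unadjusted power is 30%, 11.9 at 50%, 12.4 at 60%, 9.9 at 80%, 6.3 at 90% and 3.6 at 95%.

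**On the NIHSS scale.** With an assumed SD of 10, the difference detectable at 80% power is 2.802 × 10 × √(2/428) × √(1 − ρ²). That is 1.92 points unadjusted, 1.83 at ρ = 0.3, 1.66 at 0.5 and 1.37 at 0.7.

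**Simulation.** In 4,000 trials with 428 per arm, bivariate normal scores and ρ = 0.5, power was 78.6% for the t-test, 76.9% for Mann-Whitney, 80.1% for a change score and 89.3% for analysis of covariance. At this correlation a change score does not recover the loss.

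**Deaths before the assessment.** The figures so far assume that everyone has a score. Suppose a fraction p dies early, regardless of baseline, and is scored k survivor SDs above the survivor mean. The overall correlation becomes ρ√[(1 − p)/(1 + pk²)]. Take ρ = 0.5 in survivors and, as an illustration, a death score of 42 with survivor mean 16 and SD 8, so k = 26/8 = 3.25:
- p = 5%: correlation 0.39, gain 6.2 points.
- p = 10%: correlation 0.33, gain 4.3 points.
- p = 20%: correlation 0.25, gain 2.5 points.

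If baseline NIHSS also predicts early death (assumed odds ratio 2 per SD), simulation puts the overall correlation at about 0.45 to 0.47 and the gain at about 8 to 9 points. Across these assumptions the range is roughly 2 to 9 points.

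**The case against.** The strongest reply is that the size is conjecture. The documents give no correlation, SD, difference or power for endpoint 12, and the trial is sized for mortality alone. A reader might infer that the trial forfeits 10 points of designed power. The documents do not support that: no power was designed for this endpoint, and 10 points needs ρ near 0.5, unadjusted power near 80% and complete scores. At ρ = 0.3 the gain is under 5 points. This part of the objection stands, so the size can only be given as a range.

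Early deaths matter as well. The plan expects 29-38% mortality by day 90, and no rule is visible for patients who die before day 5-7. The missing-data heading, 12.2.4, carries no text in the public copy. Section 12.2.2 also assigns secondary indicators to the per-protocol set, so fewer than 428 per arm may contribute. This stands too. How deaths are handled may matter more for this endpoint than the choice to adjust, and the two should be settled together.

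A reader might also take chance imbalance in baseline NIHSS to mean that the planned test is biased. It is not. Under randomisation the unadjusted test is unbiased with valid type I error, and its standard error already allows for chance imbalance.

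Finally, section 12.3 is a general statement that never names NIHSS, and section 12.1.1 leaves endpoint-specific methods to a later plan. The omission is therefore not final. Until that plan exists, however, section 12.3 is the only stated method. The subgroup list does not fill the gap: it concerns the 90-day mRS and says only that the factors may affect it.

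**Conclusion.** The point holds as a modest one about efficiency. The stated methods leave baseline NIHSS out of the analysis of a later NIHSS score, and no reason is given. The consequence is lost precision on one of 17 secondary efficacy endpoints. It does not bias the comparison, inflate type I error or touch the primary conclusion.

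The size rests on assumed inputs. With 80% unadjusted power and complete scores, adjustment adds about 4 to 17 points of power for correlations of 0.3 to 0.7. A realistic allowance for early deaths ranked worst brings the gain at ρ = 0.5 down to roughly 2 to 9 points. The direction is the same in every case examined. The change is worth making because the data are already collected, not because any one of these figures is established.

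**What to change.** In section 12.3, and in the SAP to be finalised before database lock, prespecify a single main analysis for endpoint 12:

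- A proportional-odds model (or a rank-based analysis of covariance; name one in advance) with treatment and baseline NIHSS as terms.
- Deaths before the 5-7 day assessment ranked as the worst outcome.
- The adjusted treatment effect reported with its 95% confidence interval.
- The raw Mann-Whitney comparison kept as a sensitivity analysis.

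A change score should not be used as a substitute.

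The cost is a few lines of text, with no new data, visits or patients. There is a small statistical price: the proportional-odds model adds an assumption that should be checked, and its odds ratio is conditional on baseline NIHSS, which the report should say.

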The intention-to-treat analysis was chosen for statistical analysis of trial efficacy, and the per-protocol dataset (i.e., statistical analysis based on data from all patients who met the trial protocol criteria) was used as a reference. The \times 2 test or Fisher's exact probability method was used to compare event rates, while the t-test or Mann-Whitney U test was used to compare continuous variables. Superiority evaluation indicators were adopted, and statistical tests were performed at a two-sided significance level of 0.05. Differences with $P \leq 0.05$ were considered statistically significant. All statistical analyses were performed using SAS.

3. Programming and analysis of the statistical analysis system.

Trial Schedule	Serial Number	Phases	Start Date	End Date
	1	Preparation	2024-02-01	2024-07-31
	2	Execution	2024-08-01	2025-07-31
	3	Follow-up and Data Collection	2025-08-01	2025-10-31
	4	Data Processing and Analysis	2025-11-01	2025-11-30
	5	Summarizion	2025-12-01	2025-12-31

Table of contents

Lis	t of A	bbreviations	1
Stu	dy Sy	ynopsis	2
1.	Stud	dy Background	3
2.	Stud	dy Objectives	7
3.	Stud	dy Design	7
	Sele 4.1. 4.2. 4.3. 4.4.	tction of Patients, Criteria for Termination and Privacy Protection. 11 Inclusion Criteria 12 Exclusion Criteria 12 Criteria for Termination 12 Privacy Protection 12	1 2 2
5.	Sam	pple Size Calculation	3
	6.1. 6.2.	Randomization	3
	7.1. 7.2. 7.3.	Implementation of Blinding14Emergency Unblinding Procedure14Unblinding Regulations14	4 4
8.	Tre	atment	4
	8.1. 8.2. 8.3. 8.4. 8.5. 8.6.	Treatment Groups	5 5 5 6
9.	Scho	edule of Assessments	6
	9.1. 9.2. 9.3.	Collection of Baseline Data18Randomized Group18Follow-up18	8
10.	End	lpoints of the Clinical Trial	7
	10. 10.	Primary Endpoints	9 9
	10	.2.1. Secondary Efficacy Endpoints	9

The First Affiliated Hospital of Fujian Medical University

11. Adverse Events	. 20
11.1. Definition	. 20
11.1.1. Definition of Adverse Events (AE)	20

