7.3. Unblinding Regulations

This trial employs a two-step unblinding method. After blinded verification and data locking, the staff responsible for keeping the blinded data at the statistical center performs the first unblinding, informing the biostatistician of the group corresponding to each case number using the codes A and B. This allows for statistical analysis of all the data. When the statistical analysis is complete and the final report is ready, a second unblinding is conducted at the clinical summary meeting to announce the exact groups represented by A and B.

If during the trial, the entire blinded data is leaked or the rate of emergency envelope opening exceeds 20%, this double-blind trial will be considered invalid.

8. Treatment

The emergency interventional team is on standby 24 hours a day, 7 days a week. Each sub-center screens patients according to the above inclusion and exclusion criteria, assigning them to the experimental group and the control group in a 1:1 ratio. After randomization, patients receive intravenous injections of methylprednisolone sodium succinate or placebo (i.e., methylprednisolone sodium succinate simulator) treatment as soon as possible. Relevant time points (accurate to the minute) are recorded faithfully and

accurately, and the efficacy and safety of the two treatment regimens are observed and evaluated.

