12.1. Statistical Analysis Process

12.1.1. Statistical Analysis Plan

The statistical analysis plan will be discussed and developed jointly by statistical analysts and medical experts. It will be initiated before the end of the study and finalized before database lock. The plan will provide all the content to be covered by the statistical analysis, including the definition of datasets used for analysis, derived algorithms of data, and statistical description and analysis methods adopted for different indicators.

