12.2. Statistical Analysis Sets

12.2.1. Full Analysis Set (FAS)

The Full Analysis Set (FAS) includes all patients who were enrolled, randomized, and received relevant interventions. Following the principle of Intent-to-Treat (ITT) analysis, patients who did not meet the inclusion criteria, did not receive relevant interventions after randomization, or had no evaluation results should be excluded from this dataset and not included in the statistical analysis. The FAS population is used for non-inferiority evaluation analysis of the primary evaluation indicators.

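### The primary test of 90-day death is an unadjusted chi-square or Fisher test with no rule for choosing between them; naming one covariate-adjusted analysis with an interval would settle the choice and add a little power

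*Combined protocol and SAP*

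**What the plan says.** The primary efficacy endpoint is death at 90±7 days (section 10.1.1). Section 12.3 states the comparison: "Comparisons between two groups for categorical data will be made using the chi-square test or Fisher's exact test". The synopsis, under statistical analysis, names the same pair of tests, which it says "was used to compare event rates". Neither place says when one applies rather than the other, or whether the chi-square is continuity-corrected. The decision rule is P ≤ 0.05, two-sided.

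On reporting, section 12.3 says "Categorical or ordinal data will be described using frequencies and proportions". The supplied text names no risk difference, risk ratio, odds ratio, confidence interval or regression model.

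On prognostic factors, section 12.3 says "Previous studies have suggested that the following factors may affect the 90-day mRS score". It then lists ten, among them age, onset time, NIHSS, ASPECTS and occlusion site, and uses them for subgroup analysis only. Section 4.1 and Table 1 show that these five are needed for, or recorded at, screening.

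Section 12.1.1 leaves "statistical description and analysis methods adopted for different indicators" to a SAP that is to be finalised before database lock. Section 7.3 puts the A/B unblinding later: "After blinded verification and data locking, the staff responsible for keeping the blinded data at the statistical center performs the first unblinding".

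**The concern.** Two things are at stake.

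First, a primary analysis should be a single procedure fixed before the data are seen. With two tests and no rule, a result near the threshold can be significant by one and not by the other. Without a committed effect measure and interval, the plan does not say how the size and precision of the mortality effect will be presented.

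Second, the protocol itself regards several baseline variables as likely to affect the 90-day mRS, a scale on which death is one outcome. Adjusting the primary comparison for them would narrow the interval and raise power without extra patients. The plan collects them and leaves that gain unused.

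**Working it through.** **Inputs from the documents (section 5).** Mortality 38% on placebo and 29% on methylprednisolone, 1:1 allocation, two-sided α 0.05, power 80%, 856 evaluable patients (428 per arm), 5% dropout; "the maximum estimated sample size, calculated using PASS 15.0, is 902 patients" (451 per arm).

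**Reproducing the plan's figures.** With unpooled variance, n per arm = (1.960 + 0.842)² × (0.38×0.62 + 0.29×0.71) / 0.09² = (2.8016)² × 0.4415 / 0.0081 = 427.8, so 428 per arm and 856 in total. Then 856 / 0.95 = 901.05, rounded up to 902. Both figures reproduce.

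**Power of the stated tests (exact enumeration).** Uncorrected chi-square: 79.8% at 428 per arm and 82.0% at 451. Continuity-corrected chi-square, as an approximation to Fisher: 77.6% and 80.0%. The unstated choice of test is therefore worth about 2 points of power.

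**Precision.** At the design rates and 428 per arm, SE = √(0.4415/428) = 3.21 points. The expected 95% interval is 9 ± 1.96×3.21, or 2.7 to 15.3 points.

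**Can the choice change the verdict?** Two illustrative results at 428 per arm:

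| Deaths, placebo vs active | Rates | Difference (95% CI), points | P, uncorrected chi-square | P, corrected chi-square | P, Fisher |
|---|---|---|---|---|---|
| 157 vs 129 | 36.7% vs 30.1% | 6.5 (0.2 to 12.8) | 0.042 | 0.0504 | 0.0503 |
| 163 vs 124 | 38.1% vs 29.0% | 9.1 (2.8 to 15.4) | 0.005 | 0.006 | 0.006 |

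In the first row the verdict depends on the test. In the second it does not.

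**Gain from adjustment.** The documents do not say how well the baseline factors predict death, so the AUC below is an assumption and is shown as a range. If covariates explain a share R² of the outcome variance, the adjusted SE is about 3.21×√(1−R²), and power is about Φ(9/SE − 1.96), against 80.0% unadjusted by the same formula. A simulation of the proposed model was run alongside, comparing it with uncorrected chi-square on the same simulated trials.

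| Assumed AUC | R² | Adjusted SE, points | Power by formula, 428 per arm | Gain by formula | Simulated gain, 428 per arm | Simulated gain, 451 per arm |
|---|---|---|---|---|---|---|
| 0.59 | 0.023 | 3.18 | 80.9% | +0.9 | +0.8 | +0.6 |
| 0.62 | 0.040 | 3.15 | 81.6% | +1.6 | +1.7 | +1.3 |
| 0.65 | 0.063 | 3.11 | 82.5% | +2.5 | +2.5 | +2.2 |
| 0.70 | 0.112 | 3.03 | 84.4% | +4.4 | +4.6 | +4.3 |

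The simulation used age, NIHSS ≥6, ASPECTS 0–5, onset time 1–12 h and three occlusion sites, with assumed distributions and effects. It ran 40,000 trials per scenario at 428 per arm and 20,000 at 451. A second simulation with a single risk score and a logistic Wald test gave +0.9, +2.2 and +4.6 at 428 per arm and +0.4, +1.9 and +3.7 at 451 (AUC 0.59, 0.65, 0.70). Taken together: roughly 0.5 to 2.5 points at AUC 0.59 to 0.65, and about 4 to 4.5 at 0.70.

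**Validity of the adjusted test.** Simulated type I error was 4.9–5.2%, against 4.8–5.0% for chi-square; interval coverage was 94.7–95.2%. With randomisation stratified by centre and assumed centre effects (logit SD 0.5 or 0.7), the model without a centre term was conservative (4.4% or 4.0%), about the same as chi-square.

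**The case against.** An unadjusted test in a 1:1 randomised trial is valid and matches the basis of the sample size. Section 12.1.1 defers methods to the SAP, so brevity in the protocol is not an error. Deaths and percentages per arm will be reported, and anyone can compute an interval from them. By common convention Fisher is kept for small expected counts, which do not arise here, so many readers would take chi-square as intended. The power gain is small and rests on an AUC that the documents do not give. Retaining all 451 per arm adds 82.0 − 79.8 = 2.2 points by itself, and a 0.2-point difference in type I error is worth about 0.5 point of power, close to the low-end gain.

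Most of this stands. Because of the deferral, the missing estimate and interval alone would be no more than a detail for the SAP. Two things remain: the convention for choosing the test is not written down, and nor is the use of a continuity correction; and adjustment for variables already in hand is a better method at little cost.

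A reader might infer more: that the trial is underpowered, that the planned test is wrong, or that the size of the effect will go unreported. The documents support none of these. The sample sizes reproduce, the tests are valid, and proportions are promised. Nor does the 157 versus 129 example show that the tests often disagree; it shows that they can, near the threshold.

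**Conclusion.** The point holds as a modest improvement that should be made. The primary analysis is not tied to one test, and the two named tests can give different verdicts near P = 0.05. Prespecified adjustment would add roughly 0.5 to 2.5 points of power at an assumed AUC of 0.59 to 0.65. Larger gains need stronger prediction, and the entry limits (ASPECTS <6, NIHSS ≥6) may favour the low end. The figures assume covariates that are complete or simply filled, and a main-effects model that is about right; leaving out a curved age effect and an age-by-NIHSS interaction did not remove the simulated gain (+1.8 at AUC 0.62, +4.6 at 0.70). Confidence is medium, because prognostic strength is unknown.

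Three nearby matters are separate and are not part of this point: the non-inferiority wording in sections 12.2.1 and 12.2.2 ("The FAS population is used for non-inferiority evaluation analysis of the primary evaluation indicators"), the difference between the synopsis and section 6.1 on stratification by centre, and the choice of model for the mRS shift.

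**What to change.** In the SAP, before database lock and the first A/B unblinding:

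- Name one primary analysis: a superiority comparison in the intention-to-treat population, using a logistic model for 90-day death with treatment, age, baseline NIHSS, baseline ASPECTS, onset-to-randomisation time and occlusion site. Take occlusion site from pre-randomisation imaging only, since Table 1 also places DSA in the treatment period.
- Report the standardised risk difference (the primary test, two-sided 0.05) and the risk ratio, each with a 95% confidence interval.
- Keep the uncorrected chi-square test as the sensitivity analysis, and as the fallback if the model does not converge.
- Add a centre-adjusted sensitivity analysis, because the synopsis stratifies randomisation by centre.
- Do not adjust for factors that may be set after randomisation, such as anaesthesia method or TOAST class.

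Cost: small. No new data are needed. The SAP must fix in advance the covariate form (for example, linear for the continuous terms), whether ASPECTS is the site or the core-laboratory reading, and the handling of missing covariates (for example, the pooled median or mode, without using arm or outcome). Some extra programming follows. Missing 90-day outcomes need their own rule, which this change does not supply.
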